Our records for the previously approved IRB application indicate the following categories of subjects and controls are included in your research:

- Children (individuals under age 18)
- Wards of the State (Children)
- Emancipated Minors
- Students
- College of Medicine Students
- UK Medical Center Residents or

House Officers

Impaired Consent Capacity Adults

Pregnant Women/Neonates/Fetal Material

Prisoners

Non-English Speaking

International Citizens

Normal Volunteers

Military Personnel and/or DoD Civilian Employees

Patients

Appalachian Population

Please review the Subject Demographics section of your IRB application for accuracy, and note the following:

If during the course of your research 1) any prisoners have been enrolled, OR 2) subjects have been enrolled that became involuntarily confined/detained in a penal institution that have not been previously reported to the IRB, go to Subject Demographic section in your E-IRB application and mark "prisoners" in the categories of subjects to be included in the study, if it is not already marked.

Note: If either 1 or 2 above apply, and you have received funding from the Department of Health and Human Services (HHS), a Certification Letter should have been submitted to the Office for Human Research Protections (OHRP); prisoners and individuals who have become involuntarily confined/detained in a penal institution cannot continue participation in the research until OHRP issues approval. If the Certification has not been submitted, contact the Office of Research Integrity.

Based on the **total # of subjects** who have enrolled, complete the subject demographic section below:

Participant Demographics				
	Cisgender Man <small> ⓘ</small>	Cisgender Woman <small> ⓘ</small>	TGNB/TGE <small> ⓘ</small>	Unknown/Not Reported
American Indian/Alaskan Native				
Asian		2		
Black or African American		8		
Latinx		3		
Native Hawaiian or Other Pacific Islander				
White		72		
American Arab/Middle Eastern/North African				
Indigenous People Around the World				
More than One Race		10		
Unknown or Not Reported		41		

If unknown, please explain why:

Demographics are not recorded for subjects deemed ineligible.

15. Research Sites

Our records for the previously approved IRB application indicate that you are conducting research at the following sites:

UK Sites

- UK Classroom(s)/Lab(s)
- UK Clinics in Lexington
- UK Clinics outside of Lexington
- UK Healthcare Good Samaritan Hospital
- UK Hospital

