Describe the characteristics of the subject population, including age range, gender, ethnic background and health status. Identify the criteria for inclusion and exclusion.

Provide the following information:

- A description of the subject selection criteria and rationale for selection in terms of the scientific objectives and proposed study design;
- A compelling rationale for proposed exclusion of any sex/gender or racial/ethnic group;
- Justification for the inclusion of vulnerable groups such as children, prisoners, adults with impaired consent capacity, or others who may be vulnerable to coercion or undue influence.

Please consider these resources:

[NIH Diversity Policy](#)

[FDA Diversity Guidance](#) ⓘ

Based on the research question on estrogen (E2) effects on drinking in normally-cycling young women, the sample – by scientific necessity – will be exclusively women.. All women will be between ages 21 and 35 in order to assure that they have completed puberty, are premenopausal, have regularly-occurring cycles, and are roughly in the same phase of life (i.e., young adulthood). Power analyses indicate that a final sample of 100 women is sufficient to answer study questions based on an expected small to medium effect sizes, based on prior studies and our own pilot data. Our pilot data indicates that 240 women will likely need to be screened to arrive at this final sample size of 100 women. The inclusion of all women is in line with current NIH initiatives to advance understanding of health problems in women and will advance personalized assessment of mental health in women by elucidating possible ovulation-based hormonal fluctuations increasing risk for binge drinking. Therefore, the sample will be comprised completely of young women.

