AIM 2: Determine the degree to which E2 surge, associated with ovulation, increases acute sensitivity to the rewarding and disinhibiting effects of a controlled dose of alcohol. Hypothesis 2: The rewarding and disinhibiting effects of a controlled dose of alcohol (vs. placebo) will increase just before ovulation (vs. early follicular phase) concomitantly with rising estrogen.

AIM 3: Test the degree to which the E2-related changes in sensitivity to rewarding and disinhibiting effects of alcohol explain changes in women's daily drinking patterns and self-reported craving across the menstrual cycle. Hypothesis 3: E2 surge-related increases in drinking behavior will be explained by heightened sensitivity to the acute rewarding and disinhibiting effects of alcohol.

Study Design

Describe and explain the study design (e.g., observational, secondary analysis, single/double blind, parallel, crossover, deception, etc.).

- **Clinical Research:** Indicate whether subjects will be randomized and whether subjects will receive any placebo.
- **Community-Based Participatory Research:** If you are conducting [community-based participatory research \(CBPR\)](#), describe strategies for involvement of community members in the design and implementation of the study, and dissemination of results from the study.
- **Qualitative research:** Indicate ranges where flexibility is needed, if a fixed interview transcript is not available, describe interview topics including the most sensitive potential questions.
- **Research Repositories:** If the purpose of this submission is to establish a Research Repository (bank, registry) and the material you plan to collect is already available from a commercial supplier, clinical lab, or established IRB approved research repository, provide scientific justification for establishing an additional repository collecting duplicate material. Describe the repository design and operating procedures. For relevant information to include, see the [UK Research Biospecimen Bank Guidance](#) or the [UK Research Registry Guidance](#).

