Laboratory Testing of Alcohol Sensitivity: Participants attend two identical laboratory sessions to test sensitivity to the rewarding and disinhibiting effects of a controlled dose of alcohol, once during the early follicular phase and once during the late follicular phase. Testing will start between 11:00am-6:00pm. Participants will be required to fast for four hours and abstain from drug use before test sessions. At session outset, breath and urine samples will be obtained to verify a zero blood alcohol concentration (BAC), recent use of benzodiazepines, barbiturates, cannabis, cocaine, amphetamine, and opiates, and also to confirm that women are not pregnant. The alcohol dose consists of 0.60 g/kg absolute alcohol that produces a peak blood-alcohol concentration (BACs) of 80 mg/dl. The dose was chosen based on prior research showing that it elevates levels of reward and impairs inhibitory control in young women. We have extensive experience with this dose and its pharmacokinetics are well-known. Doses are mixed with a carbonated, non-caffeinated, lemon flavored soda and are consumed in 10 minutes. The placebo consists of 300 ml of lemon flavored soda with a small amount (i.e., 3 ml) of alcohol floated on the top of the beverage.

The test battery consists of measures of rewarding effects and alcohol effects on disinhibition and impulsive choice. The task battery is brief (30 minutes) to accommodate repeated testing and prevent fatigue. Also, its brief duration minimizes change in BAC during testing. Baseline measures of subjective reward and disinhibition/impulsivity will first be assessed at each test session. For baseline assessment, volunteers receive a placebo (non-alcoholic beverage) and then complete the test battery. Volunteers then receive the active dose and repeat the test battery at approximately 30 minutes after drinking when their ascending BAC reaches 60 mg/dl with the

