primary contact with NIAAA. [name] will direct the longitudinal assessments and analyses of women's hormonal fluctuation and daily drinking patterns, including oversight of the integrity and reliability of data collection protocols and data analysis. [name] will train and supervise technical assistants who are involved in hormonal assays and ecological assessments of drinking patterns and other drug use. Drs. [name] and [name] will jointly participate in disseminating research results at scientific conferences and manuscript and grant preparation from data arising from this project. Due to the intensive nature of 35 longitudinal days of data collection and scheduling of laboratory cognitive visits based on individualized information about participant cycle phase, there will be a project coordinator. The project coordinator will coordinate all participant scheduling, follow-up, retention and preliminary data entry and management tasks. Her duties will include sending daily reminders, scheduling laboratory visits, mailing and emailing questionnaires, handling retention methods, including participant payment, data entry management and analysis, and communicating with all staff. [name] will train and supervise the project coordinator and coordinate these research activities with [name] Research Laboratory. [name] will also coordinate communications between key project personnel and non-project personnel who are essential to project completion.

Co-investigator [name] will provide medical supervision on the project and will oversee procedures for screening of potential subjects and safety of laboratory volunteers. [name] is Chair of the University's Psychiatry department, which will also provide 24 hour, on-call, medical consultation and support for the project. [name] will also assist in interpretation of findings and publication of results. Other team members include: [name], an expert in hormonal mechanisms who will oversee hormonal assays. Consultant [name] is an expert in multilevel modeling of menstrual cycle and ovarian steroid effects on behavior. Publication authorship will be based on the relative scientific contributions of the PIs and key personnel.

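### Are 100 women too few for Aim 3 at the small to medium effects the plan expects?

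*Combined protocol and SAP*

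**What the plan says.** The only sample-size justification in the visible text is in the description of the subject population (Subject Demographics section): "Power analyses indicate that a final sample of 100 women is sufficient to answer study questions based on an expected small to medium effect sizes". The sentence goes on to attribute those effects to prior studies and the investigators' own pilot data. The next sentence expects about 240 women to be screened to reach the final 100, so 100 is already net of losses.

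The Objectives section sets three aims. Aim 2 compares the effects of alcohol against placebo between the early and late follicular phases. Aim 3 tests the degree to which "the E2-related changes in sensitivity to rewarding and disinhibiting effects of alcohol explain changes in" daily drinking and craving. Under Research Procedures, "Participants attend two identical laboratory sessions to test sensitivity to the rewarding and disinhibiting effects of a controlled dose of alcohol", one session in each phase. Daily drinking and craving are reported for 35 days.

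The visible text states no alpha, sidedness, target power, numerical effect size or model for any aim. The Resources section says that the consultant "is an expert in multilevel modeling of menstrual cycle and ovarian steroid effects on behavior". The Funding/Support section lists a grant file as an attachment, which is not reproduced.

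**The concern.** The sufficiency claim is unqualified, covers all the study questions, and labels no aim exploratory. Aim 3 is the most demanding of them. The 35 diary days sharpen each woman's drinking change but add no sensitivity changes, so a within-woman link rests on about 100 independent units. If small to medium is read as r = 0.1 to 0.3 and the midpoint is taken, a two-sided 5% test would miss a true link about half the time. Hypothesis 3 is also a mediation claim, and an indirect effect that needs two paths cannot have more power than the weaker one.

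What would be at stake is the reading of a null result. If a sample called sufficient shows no Aim 3 link, readers may conclude that sensitivity does not explain drinking, when the study had only even odds of seeing a modest link.

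**Working it through.** **Inputs.** From the documents: 100 women in the final sample; two laboratory sessions, hence one sensitivity change per woman per measure; expected effects described only in words. Assumed, because the documents do not give them: two-sided 5%, 80% power as a reference, and a single woman-level correlation as the Aim 3 test.

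**The plan's own figure.** It cannot be reproduced. The sentence gives 100 and the phrase small to medium, with no power, alpha or numerical effect, so there is no stated result to compare with a recalculation.

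**Aim 3, single path.** Fisher z: power = Φ(atanh(r)·√(n − 3) − 1.96) plus the opposite tail, with √97 = 9.849.

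| r | atanh(r)·9.849 | power |
|---|---|---|
| 0.10 | 0.988 | 16.7% |
| 0.20 | 1.997 | 51.5% |
| 0.30 | 3.048 | 86.2% |

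A 200,000-run simulation gives 51.7% at r = 0.2, and one-sided 5% gives 63.8%. The smallest r with 80% power is tanh((1.960 + 0.842)/9.849) = 0.277.

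**Aim 2, paired contrast.** Noncentral t with 99 degrees of freedom and noncentrality dz·√100: 50.8% at dz = 0.20, 84.4% at 0.30, 93.4% at 0.35. Power reaches 80% at dz = 0.283.

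**How far the 52% depends on the metric.** The plan names none. Taking the middle of the conventional small and medium benchmarks (also an assumption):

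- r scale: (0.1 + 0.3)/2 = 0.20, power 51.5%.
- r-squared scale: (0.01 + 0.09)/2 = 0.05, so r = √0.05 = 0.224. Then atanh(r)·9.849 = 2.240 and power is about 61%.
- f-squared scale: (0.02 + 0.15)/2 = 0.085, so r = √(0.085/1.085) = 0.280. Then atanh(r)·9.849 = 2.833 and power is about 81% (82% by noncentral F).

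The same phrase therefore gives anything from about 52% to 81%.

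**How far it depends on the model.** Sensitivity is measured by subjective ratings, attentional bias and a go/no-go task. Suppose two change scores each correlate 0.2 with the outcome. An equal-weight composite then correlates 0.4/√2 = 0.283 if they are mutually uncorrelated (power about 82%), or 0.4/√2.6 = 0.248 if they correlate 0.3 (about 71%). Testing several measures separately with a multiplicity correction would lower power instead. A multilevel model with sensitivity centred within woman adds no changes: a small simulation gave 53% at r = 0.2. A model pooling within- and between-woman differences gave about 82%, but it also rejected 31% of the time when the within-woman link was zero and the between-woman r was 0.2, so it answers another question.

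**Recruitment.** The continuation review reports 136 enrolled, 41 of them without demographics because "Demographics are not recorded for subjects deemed ineligible". That leaves 2 + 8 + 3 + 72 + 10 = 95, an upper bound on the eligible women enrolled by then; completers are not reported. At n = 95, power at r = 0.2 is 49.4%, so the picture is the same.

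**The case for a change.** The strongest case for a change is that the claim is universal, while under conventional assumptions 100 women are clearly too few for part of the range it covers. At r = 0.1 power is 17%, and at dz = 0.20 it is 51%. One-sided testing does not rescue r = 0.2, and a mediation test would do no better than the single path. Replacing the sentence with the smallest detectable effect for each aim would cost only wording and would help a later reader judge a null result.

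The arithmetic stands, and so does the observation that sufficiency is not shown toward the small end. The step from there to a defect does not. The choice of r = 0.2, two-sided 5% and a single path is the reader's, and the midpoint argument fails on the f-squared scale. The plan says the expected effects are "based on an expected small to medium effect sizes, based on prior studies and our own pilot data", so a benchmark midpoint replaces estimates that exist but are not visible. The sentence answers an ethics-form prompt about the study population and reports that power analyses were done. Their inputs may well be in the grant file, so absence here does not show absence from the planning. Nor do the documents require Aims 2 and 3 both to succeed, so multiplying their powers has no basis.

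The benefit for reading a null result is also slight. The confidence interval does that work: with 100 women, an observed correlation of zero has a 95% interval of ±tanh(1.96/9.849), or about −0.20 to 0.20, whatever the planning sentence says.

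**Conclusion.** No change follows. The sentence is loose, but it contains no figure that the design contradicts. Assuming two-sided 5% and a single woman-level path, Aim 3 power with 100 women runs from 17% at r = 0.1 to 86% at r = 0.3. The middle of small to medium gives about 52%, 61% or 81% depending on whether effects are measured as r, r-squared or f-squared. Aim 2 runs from 51% at dz = 0.20 to 93% at dz = 0.35. Both aims reach 80% at about 0.28 on their own scale. The claim is therefore reasonable over the upper part of the range and unsupported near its lower end.

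This is missing detail in a summary statement. Supplying it would alter neither the sample size, the conduct nor any analysis. Wording built on assumed inputs would put a reader's choices of alpha, power and model into the protocol in place of the investigators' own. The conclusion would differ if the underlying power analysis turned out to rest on an Aim 3 effect well below r = 0.28, which the visible documents do not allow anyone to check.

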Alcohol use poses significant health problems particularly when characterized by bouts of heavy consumption (i.e., binges). It is now recognized that women demonstrate greater vulnerability to the adverse effects of alcohol, including greater physiological risk of organ damage (e.g., liver cirrhosis), than do men with comparable histories of alcohol use. Research suggests that ovarian hormones play a role in substance abuse. With regard to alcohol use, there is evidence to suggest that women may exhibit distinct patterns of heavy drinking across the menstrual cycle. Indeed, our preliminary research shows that surges in follicular estradiol [E2] at ovulation predict increased alcohol use in young women. Yet, to date no research has aimed to determine the specific behavioral mechanisms by which rapid surges in E2 confer increased abuse potential of alcohol. The proposed study directly examines ovarian hormone flux and acute sensitivity to alcohol to provide the first rigorous and integrative test of the hypothesis that rapid rises in estradiol increase the acute rewarding and disinhibiting effects of alcohol and that this heightened sensitivity increases alcohol use outside the laboratory. A sample of 100 naturally-cycling women will be examined daily over their menstrual cycle using an integrative combination of daily ecological assessments of hormone fluctuations and alcohol use along with strategically-timed laboratory tests of their acute sensitivity to the rewarding and disinhibiting effects of a controlled dose of alcohol. The findings will advance understanding of the neurobehavioral mechanisms linking E2 to alcohol abuse and inform clinical assessment practice by highlighting the importance of menstrual cycle phase and hormonal profiles when assessing alcohol abuse risk in young women. Heavy episodic or binge drinking is often cited as one of the top public health issues and is a particular problem among college students, affecting more than 6 million of them with negative consequences including unsafe sexual activity and assaults. Notably, substance abuse in women is on the rise, and animal research suggests that females exhibit distinct patterns of acquisition, maintenance, and relapse, as well as particularly troublesome functional and health consequences compared to men. Yet, women remain especially understudied. Although animal research suggests that ovarian hormones play a role in substance abuse, and aspects of substance abuse appear to vary cyclically across the monthly reproductive cycle in women, no work to date has evaluated cyclical hormonal associations with alcohol abuse in young adult women. The proposed research advances the field in a new direction by integrating the study of monthly hormonal fluctuations in young women with rigorous laboratory tests of their sensitivity to alcohol effects implicated in its abuse potential (e.g., rewarding, disinhibiting effects). Our pilot data suggests sex differences in sensitivity to the rewarding effects of alcohol in a controlled laboratory tests and further indicates that rapid surges in follicular estradiol [E2] around ovulation, when progesterone is low, predict dramatically increased alcohol use, an estimated 200% increase in units of alcohol consumed the next day. This is consistent with our empirically-supported scientific premise and theoretical model that ovulation, like puberty, enhances risk-taking behaviors, particularly in impulsive women. Yet, to date no research has aimed to determine the specific behavioral mechanisms by which rapid surges in E2 confer increased abuse potential of alcohol around ovulation. Such information would be critical for informing personalized intervention efforts for binge drinking in vulnerable young women.

The proposed longitudinal study builds on our relevant preliminary research with an integrative, mechanistic investigation that combines ecological daily assessments of hormone fluctuations and alcohol use with strategically-timed laboratory tests of acute sensitivity to the rewarding and disinhibiting effects of alcohol across to determine the behavioral mechanism by which E2 can affect drinking behavior in women. A short-term longitudinal study of 100 women will collect daily measures of hormone levels and alcohol use and conduct laboratory tests of sensitivity to the rewarding and disinhibiting effects of a controlled dose of alcohol at key points of the menstrual cycle. The daily saliva and self-report data will allow for a fine-grained investigation of the lagged correlations between E2 and daily alcohol use patterns and alcohol craving across the entire menstrual cycle. The two laboratory visits will test and compare the acute sensitivity to the rewarding and disinhibiting effects of a controlled dose of alcohol during the early follicular phase when E2 is low to the late follicular phase when E2 is rising. This work will provide the first rigorous integrative test of the hypothesis that rapid rises in estradiol increase rewarding and disinhibiting effects of a controlled dose of alcohol and that such increased sensitivity predicts with increased alcohol use outside the laboratory. Elucidation of the behavioral mechanisms by which estradiol surges can increase alcohol use would provide a critical advancement of neurobiological theory of alcohol abuse in women, an understudied area, as well as provide new directions for personalization of alcohol abuse treatment in women. Specifically, this work may suggest the need for hormone-stabilization intervention (e.g., oral contraceptives) for young women at risk for binge drinking, and identify cycle phases in which those in treatment might be more likely to relapse.

Objectives

List your research objectives. Please include a summary of intended research objectives in the box below.

AIM 1: Determine the degree to which phases across the menstrual cycles predict changes in ecological daily drinking patterns and self-reported craving. Hypothesis 1: Craving and alcohol intake will increase just prior to ovulation (during late follicular phase vs. early follicular phase) concomitantly with rising estrogen.

AIM 2: Determine the degree to which E2 surge, associated with ovulation, increases acute sensitivity to the rewarding and disinhibiting effects of a controlled dose of alcohol. Hypothesis 2: The rewarding and disinhibiting effects of a controlled dose of alcohol (vs. placebo) will increase just before ovulation (vs. early follicular phase) concomitantly with rising estrogen.

AIM 3: Test the degree to which the E2-related changes in sensitivity to rewarding and disinhibiting effects of alcohol explain changes in women's daily drinking patterns and self-reported craving across the menstrual cycle. Hypothesis 3: E2 surge-related increases in drinking behavior will be explained by heightened sensitivity to the acute rewarding and disinhibiting effects of alcohol.

Study Design

Describe and explain the study design (e.g., observational, secondary analysis, single/double blind, parallel, crossover, deception, etc.).

- **Clinical Research:** Indicate whether subjects will be randomized and whether subjects will receive any placebo.
- **Community-Based Participatory Research:** If you are conducting [community-based participatory research \(CBPR\)](#), describe strategies for involvement of community members in the design and implementation of the study, and dissemination of results from the study.
- **Qualitative research:** Indicate ranges where flexibility is needed, if a fixed interview transcript is not available, describe interview topics including the most sensitive potential questions.
- **Research Repositories:** If the purpose of this submission is to establish a Research Repository (bank, registry) and the material you plan to collect is already available from a commercial supplier, clinical lab, or established IRB approved research repository, provide scientific justification for establishing an additional repository collecting duplicate material. Describe the repository design and operating procedures. For relevant information to include, see the [UK Research Biospecimen Bank Guidance](#) or the [UK Research Registry Guidance](#).

Subjects will attend a diagnostic visit to assess baseline clinical characteristics. In addition, subjects will attend two laboratory visits to test alcohol sensitivity at two key points in the cycle: during the early follicular phase when E2 is low and the late follicular phase when E2 is rising. Every day after their first laboratory visit for 35 consecutive days, women will provide saliva samples each morning to assess hormonal levels and complete a self-report on their drinking behavior and alcohol craving every evening through a secure online server.

The daily saliva and self-report data will allow for a fine-grained investigation of the lagged correlations between E2 and daily alcohol use patterns and alcohol craving across the entire menstrual cycle. The two laboratory visits will test and compare the acute sensitivity to the rewarding and disinhibiting effects of a controlled dose of alcohol during the early follicular phase when E2 is low and the late follicular phase when E2 is rising. After screening, study volunteers will be followed daily in order to assess when they start their next menstrual cycle (i.e., the day they start bleeding). Within 1-2 days of that point, volunteers are scheduled to attend their initial diagnostic visit. Participants are then counterbalanced to begin the study during either their early follicular phase (approximately day 5) or their late follicular phase (approximately day 12) which is also when they begin their 35 days of consecutive daily data collection. This serves to counterbalance the order of the two alcohol sensitivity test sessions: early follicular versus late follicular phase. Ovulation testing and daily salivary E2 will confirm the proximity of the late follicular phase to ovulation, with the goal of ovulation occurring 1-3 days after the late follicular visit, and capturing a higher, rising E2 level in the late follicular phase relative to a lower level in the early follicular phase. We overrecruit in order to assure analyses are appropriately powered and reliable.

Attachments

Subject Recruitment Methods & Advertising

Describe how the study team will identify and recruit subjects. Please consider the following items and provide additional information as needed so that the IRB can follow each step of the recruitment process.

- How will the study team identify potential participants?
- Who will first contact the potential subjects, and how?
- Will you use advertisements? If so, how will you distribute those?
- How and where will the research team meet with potential participants?
- If applicable, describe proposed outreach programs for recruiting women, minorities, or disparate populations.
- How will minimize undue influence in recruitment?
- Attach copies of all recruiting and advertising materials (emails, verbal scripts, flyers, posts, messages, etc.).

For additional information on recruiting and advertising:

- [IRB Application Instructions - Advertisements](#)
- [PI Guide to Identification and Recruitment of Human Subjects for Research](#)

The study will recruit subjects through flyers, brochures, posters, Research Spotlights, ads placed on campus and in the surrounding community and region (Study Team will place/remove ads), including but not limited to the UK Medical Center, UK Clinics, Good Samaritan Hospital, Student Center, UHS, the 5 UK Center for Clinical and Translational Research wall mounts, Cardinal Hill, monitor screens, and area facilities and businesses. Subjects may be recruited through paid print and digital advertisements, including brochures, magazines, newspaper (e.g., Herald Leader, Bluegrass Area, Courier Journal, Cincinnati Enquirer, Health & Wellness, Chevy Chaser, Hamburg Journal, Business Lexington, or other publications in the surrounding region e.g., Bluegrass Regional print & digital ads, may include Appalachian counties), Radio (e.g., Sirius, Clear Channel, Cumulus, LM Communications, Public Radio,

Pandora, etc.), Television spots, scrolling information on community stations, and theater screens. Recruitment ads may also appear on billboards, Lextran buses, taxicabs, other transportation methods, and Craig'sList. The study will employ a pre-screening eligibility survey to determine if a volunteer meets basic inclusion/exclusion criteria. We will build and administer the eligibility survey on UK's REDCap which provides HIPAA compliant storage on UK servers and encrypted transmission of survey responses. The link will be included in study information sent to ResearchMatch participants who have indicated interest in the study. Before redirecting the volunteer outside of ResearchMatch and to the REDCap survey, the volunteer is once again asked to confirm their interest in completing the pre-screening survey. All advertisements will be approved by the UK Institutional Review Board (IRB) and the UK Office of Public Relations. Interested individuals will contact the experimenter by email. A general description of the study and the criteria for participation will be explained. The general requirements of the tasks will be described. It also will be explained that a participant must fast for 4 hours prior to test sessions. Prospective subjects are also told that a moderate dose of alcohol will be administered during two laboratory visits so that alternate transportation home is provided. The following initial inclusion criteria will be obtained as preliminary screening to be verified at the intake session: i) Confirmation of Age (21-35). Volunteers will be told to bring proof of age to the laboratory (e.g., driver's license or passport). ii) General Health Status. It will be explained that volunteers must be naturally cycling, not currently taking hormones, and not have any serious health problem that is contraindicated by alcohol use. iii) Drinking Status. It will be explained that all volunteers must be alcohol drinkers, who consume alcohol at least once per week. No abstainers will be tested. iv) No History of Drug or Alcohol Dependence. It will be explained that individuals in drug/alcohol treatment, or who have sought treatment, cannot participate. Volunteers will then respond to questions from the AUDIT. v) Pregnancy. Women will be asked if they are currently pregnant or breast feeding. It will be explained that no pregnant women or women who are breast feeding can participate in the study. Women will be told that they will be required to submit to a simple urine sample-pregnancy test (testing human chorionic gonadotrophin (HCG) levels) and that a non-negative result would disqualify them from participation. vi) Drug-urine Screen. It will be explained to subjects that they must submit a urine sample prior to each session that will be screened for other drug use that would disqualify them from participating. vii) Zero BAC Check. Volunteers will be informed in advance that they must have a zero BAC and will be given a breath test when they arrive for laboratory testing. viii). Any persons excluded from participation during screening will simply be thanked for their interest. Appropriate volunteers will be scheduled and instructed to abstain from alcohol and other drugs for 24 hours. They will also be instructed to fast for 4 hours prior to arrival for the laboratory test sessions which will always occur in the afternoon. Upon arriving at the lab, all participants' proof of age will be checked and each will be asked to sign an informed consent form describing the nature of the experiment and outlining all of the conditions for participation.

Women ages 21-35 years who drink at least weekly and who are naturally cycling and not currently taking hormones are invited to participate in the study. This study will be advertised on recruitment internet webpages in digital or video form (e.g., UKclinicalresearch.com, ResearchMatch.org, CenterWatch.com, CISCRP, UK, CCTS and may utilize Google Adwords). The study will be promoted via social media, including Facebook boost ads, UK_CCTS Facebook, UK_CCTS Twitter, UK_CCTS Instagram, UK and UKHC social media, and departmental/lab pages. If advertised on UKClinicalresearch.com, the online study flyer will include an option for interested individuals to enter and submit their contact information, they will be asked whether study team can contact them (Yes or No) via study-related text messages, and CCTS will also ask, 'How did you learn about the study? Internet and social media recruitment will follow the terms of use for each site utilized. The study will also be promoted through UK HC monitor screens. Potential participants may be identified from registry databases, including but not limited to ResearchMatch.org, Wellness Health and You, Sanders Brown Center on Aging, Infectious Disease, Dentistry, and the Markey Cancer Center. The CCTS attends outreach activities to promote research participation in general (e.g., Roots & Heritage Festival, Latino Festival, Eastern Kentucky University, Transylvania Health fairs, etc.) and will bring all relevant study flyers that are enrolling participants. This study may also go out on email distribution, listservs, or e- newsletters, e.g., the CCTS list serv, Markey Cancer Affiliates list servs, ResearchMatch.org, Wednesday's Word, Kentucky Office of Rural Health (KORH), Appalachian Translational Research Network (ATRN), etc. We may utilize physician referral letters to community physicians for patient recruitment. Articles and interviews about the researchers and research study may be promoted via UKNow, Kentucky living, and other media outlets. Research and study-related articles published on UKNow may contain standard language directing interested individuals on where to read more about research and current studies. UKPR, UK HealthCare marketing or the CCTS PRS may create videos to promote research, researchers and their studies to local, regional and national media venues and on internal hospital monitors. UK HealthCare may place study recruitment flyers on their internal and external racks (e.g., UK pharmacies, clinics, UK Libraries and Lexington Libraries) or on digital monitors. Participants may be recruited using newsletters, such as In the Loop, Health Matters, Making a difference, and external news letters. The study may also be advertised through UKPR and UKHC outreach activities. All of these sources will be used to recruit participants from the Lexington area and surrounding counties. Interested individuals will contact the project coordinator by email to complete screening. All advertisements will be approved by the UK Institutional Review Board (IRB) and the UK Office of Public Relations. The investigators have extensive experience using this recruitment procedure in communities for alcohol and other drug studies and have recruited over 5000 participants using this method in the past 25 years.

Attachments

Attach Type	File Name
Advertising	Hormone grant GeneralFlyer PR edits STAMPED.pdf

Research Procedures

Describe how the research will be conducted.

- What experience will study participants have?
- What will study participants be expected to do?
- How long will the study last?
- Outline the schedule and timing of study procedures.
- Provide visit-by-visit listing of all procedures that will take place.
- Identify all procedures that will be carried out with each group of participants.
- Describe deception and debrief procedures if deception is involved.

Differentiate between procedures that involve standard/routine clinical care and those that will be performed specifically for this research project. List medications that are explicitly forbidden or permitted during study participation.

